10.2 Study Population Definitions

10.2.1 Treated Population

The Treated population will consist of all enrolled subjects who received at least one dose of study drug. It is equivalent to the Safety population. The Treated population will be used for the primary efficacy and safety analyses for this single arm Phase 2 study. Treated population will be used (instead of Safety population) for the rest of the protocol.

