Blood samples will be collected for intensive sampling in all 30 subjects in order to estimate the PK of ATG-008 and metabolites in Asian subjects.

As for the 2 dose groups 45 mg/QD and 20 mg/BID, PK samples of 10 subjects each should be collected to further evaluate the PK profile of ATG-008 and its metabolites.

Overview of Exposure-Response Analyses

Exposure-response analyses will be performed to evaluate relationships between ATG-008 and/or M1 exposure and clinical outcomes of efficacy and safety.

Statistical Summary

The primary efficacy endpoint is ORR, and the primary analysis population for both efficacy and safety analysis is the Treated population.

All efficacy and safety results will be tabulated and/or summarized using for the Treated population by treatment arm.

TABLE OF CONTENTS

MEDICAL / EMERGENCY CONTACT INFORMATION.....	2
PROTOCOL SYNOPSIS.....	5
TABLE OF CONTENTS.....	12
LIST OF TABLES	15
LIST OF FIGURES.....	15
1. INTRODUCTION	20
1.1. Hepatocellular Carcinoma	20
1.2. Mammalian Target of Rapamycin	22
1.2.1. Hepatocellular Carcinoma and mTOR.....	22
1.3. ATG-008.....	23
1.3.1. ATG-008 Preclinical Data.....	23
1.3.2. ATG-008 Clinical Data	25
1.4 Study Rationale.....	31
1.4.1 Rationale for Dose of ATG-008	32
2. STUDY OBJECTIVES	34
2.1 Primary Objective	34
2.2 Secondary Objectives.....	34
3. STUDY ENDPOINTS	34
3.1 Primary Endpoint.....	34
3.2 Secondary Endpoints	34
4. OVERALL STUDY DESIGN	34
4.1 Study Design.....	34
4.2 Study Design Rationale.....	36
4.3 Study Duration	37
4.4 End of Trial	38
5. TABLE OF EVENTS.....	39
6. PROCEDURES.....	43
6.1. Screening Period	43
6.2. Treatment Period.....	45
6.2.1 End of Treatment.....	46
6.3. Follow-up Period	46
6.3.1 28-day Follow-up.....	46
6.3.2 Efficacy Follow-up	46
6.3.3 Survival Follow-up	46
6.4. Response Assessments	46
6.4.1 Assessment of Radiologic Response According to RECIST 1.1	47
6.5. Pharmacokinetics	47
6.5.1 Intense Blood Sampling.....	48
6.5.2 PK urine collection	48
7. STUDY POPULATION	49
7.1 Number of Subjects.....	49
7.2 Inclusion Criteria	49
7.3 Exclusion Criteria	50
8. DESCRIPTION OF STUDY TREATMENTS.....	52
8.1 Description of Investigational Product(s)	52
8.2 Treatment Administration and Schedule	52

8.2.1	Treatment modification	52
8.2.2	Overdose	54
8.3	Method of Treatment Assignment	54
8.4	Packaging and Labeling	54
8.5	Investigational Product Accountability and Disposal	54
8.6	Investigational Product Compliance	55
9.	CONCOMITANT MEDICATIONS AND PROCEDURES	55

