1.4 Study Rationale

There remains a high unmet medical need for effective therapies for subjects with unresectable HCC refractory to, or following failure of, at least one prior line of systemic therapy. A strong biologic rationale exists for targeting of the mTOR pathway in HCC, in particular inhibition of pAKT. ATG-008, an mTOR kinase inhibitor targeting both TORC1 and TORC2 complexes, has demonstrated promising preclinical and clinical activity against HCC, especially in HBV+ HCC subjects. Furthermore, resistance to sorafenib can be mediated by mTOR pathway activation lending further support to the development of ATG-008 in unresectable HCC in the second-line setting.

As described earlier, the greatest incidence and mortality of HBV+ HCC patients are in Asian countries (especially in China), and this contrasts sharply with western countries. It is critical to have effective treatment for patients failed at least one prior line of systemic therapy in Asian subjects.

- **Clinical efficacy: compared to the study results of Celgene, the current preliminary clinical study data of this study showed that ATG-008 treatments with 15 mg and 30 mg were effective, but the expected tumor control rate had not been observed yet. It was preliminarily considered that the best dose range of ATG-008 might have not been achieved.**

According to the results of study CC-223-ST-001-B which has been completed by Celgene, the ORR of solid tumor HCC cohort was 5.7% (3/53), among which, the best efficacy of 3 subjects (all had positive HBV) was PR and 2 of them were treated with 45 mg/QD ATG-008 (the maximum tolerated dose [MTD] of ATG-008 monotherapy was 45 mg/day, the intolerable dose was 60 mg/day).

As of 18 Jul 2019, the preliminary clinical study data showed that this study enrolled a total of 35 HCC subjects (all were Asian, among which, 15 subjects were from Chinese mainland, 13 from

Korea and 7 from Taiwan. 7 subjects received oral ATG-008 at the initial daily dose of 15mg and 28 subjects received 30mg). Among 35 subjects, 1 subject achieved PR, 14 subjects achieved SD, 19 subjects achieved PD and 1 subject still received the first cycle of treatment and no efficacy evaluation has been performed yet. The survivors accounts for approximately 65.7% (23/35). The diameter of the targeted lesions of tumors decreased after treatment from baseline in 38.2% (13/34) subjects. Currently, subjects who received the longest treatment had completed 11 cycles of treatment.

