10. STATISTICAL ANALYSES

10.1 Overview

This is an Asian multi-regional clinical trial (MRCT) in which ATG-008 will be administered orally to hepatitis B positive (HBV+) HCC subjects who have received at least one prior line of systemic therapy.

According to the previous study results, the sponsor will plan to continue to enroll approximately 40 hepatitis B virus (HBV) positive, unresectable HCC subjects who have received at least one prior line of systemic therapy. Among which, approximately 20 subjects will receive oral ATG-008 at an initial dose of 45 mg/QD and another 20 subjects will receive oral ATG-008 at an initial dose of 20 mg/BID. The pharmacokinetic (PK) samples will be collected from 10 subjects each in the two dose groups so as to further evaluate the PK profile of ATG-008 and its metabolites.

If ORR of tumor is greater than 15% in the study dose group (45 mg/QD or 20 mg/BID), this study will be expanded to enroll additional approximately 110 subjects using ORR as the primary study endpoint, to further evaluate the efficacy and safety of ATG-008.

It is designed as an open-label phase 2 trial evaluating the pharmacokinetics (PK), tolerability and efficacy of oral ATG-008 administered daily until the radiologic disease

progression (according to RECIST 1.1) or intolerable toxicity.

The sections below provide an overview of the proposed statistical considerations and analyses. The final statistical analysis methods will be documented in detail in the Statistical Analysis Plan (SAP).

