10.3 Sample Size and Power Considerations

For the primary efficacy endpoint, ORR, the sample size is based on one-sample binomial test with normal approximation. The null hypothesis to be tested is that the ORR (defined as the proportion of subjects with at least a partial response (PR) based on the Treated population subjects) is $\leq 10\%$; the alternative hypothesis is that the ORR is $\geq 18\%$. With these hypotheses, a sample size of 130 (20+110) subjects in the Treated population would provide 80% power at a one-sided 0.025 significance level. This criterion requires that the lower limit of the 95% confidence interval (CI) for the ORR is greater than 10%.

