10.6.1 Analysis of the Primary Efficacy Endpoint

Overall response rate (ORR) is the primary efficacy endpoint. A responder is any subject who achieves a CR or PR. ORR is defined as the percentage of subjects that achieve a CR or PR.

ORR will be summarized with 95% confidence interval (CI), and tested using one sample binomial test for the Treated population analyzed in a similar way as for DCR. Subgroup analysis for ORR will be performed for subgroups specified in Section 10.6.3.

ORR with 95% confidence intervals will also be provided for the per-protocol population.

The primary analysis for ORR will be performed at approximately 3 months after the last subject is first dosed. All other endpoints will be analyzed at the same time. The analysis will be updated at 12 months after the last subject's first dose date.

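### The primary ORR test set has two sizes: about 185 as defined in 10.2.1 and tested in 10.6.1, but 130 as powered in 10.3

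*Combined protocol and SAP*

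**What the plan says.** Four places in the combined protocol bear on which subjects enter the primary ORR test.

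- **Section 10.2.1** defines the set: "The Treated population will consist of all enrolled subjects who received at least one dose of study drug". It equates this set with the Safety population and gives it its role: "The Treated population will be used for the primary efficacy and safety analyses for this single arm Phase 2 study".
- **Section 10.6.1** states that ORR will be "tested using one sample binomial test for the Treated population". No dose group or study part is named.
- **Section 10.3** sizes the test of ORR at most 10% against at least 18%, one-sided 0.025, 80% power, at "a sample size of 130 (20+110) subjects in the Treated population".
- **Section 10.1** sets the expansion rule by dose group: "If ORR of tumor is greater than 15% in the study dose group (45 mg/QD or 20 mg/BID), this study will be expanded", with about 110 more subjects.

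Section 7.1 gives the counts: 35 already enrolled (15 mg and 30 mg), about 40 more (45 mg QD and 20 mg BID, about 20 each), and about 110 if the study expands. The synopsis adds, under Statistical Summary, "All efficacy and safety results will be tabulated and/or summarized using for the Treated population by treatment arm".

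**The concern.** One defined term covers two different sets. By its definition, the Treated population after one expansion is every dosed subject at any regimen, about 185. By its use in 10.3 it is 130, which can only be one new dose group of 20 plus its expansion of 110. Sections 10.2.1 and 10.6.1 are the rules an analyst would program from, and neither restricts the test to the expanded regimen.

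The difference matters because the extra 55 subjects are not exchangeable with the 130. The 35 first-part subjects received doses at which, according to section 1.4, the expected tumour control had not been seen. The July 2019 count there was "1 subject achieved PR, 14 subjects achieved SD, 19 subjects achieved PD and 1 subject still received the first cycle of treatment". The other 20 received the new regimen that was not expanded. Pooling them could make an expanded regimen that meets the 10.3 criterion fail the primary test. Two analysts following different sections could report opposite primary conclusions from the same data. The trial is open-label and ORR is inspected at the expansion decision, so a choice of set made later would be made with responses by dose already known.

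**Working it through.** **1. The plan's own figure.** Inputs from 10.3: p0 = 0.10, p1 = 0.18, one-sided 0.025, power 80%, normal approximation.

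n = [(1.960·√(0.10·0.90) + 0.842·√(0.18·0.82)) / 0.08]² = 129.8, so 130. Power at 130 is 80.1%. The figure reproduces; the sizing is correct and the 130 is not a misprint.

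**2. The literal set.** From 7.1: 35 + 40 + 110 = 185, which is 55 (42%) more than 130. This assumes one expansion and that every enrolled subject is dosed.

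**3. Critical counts against 10%.** The z-test needs at least 0.10n + 1.960·√(0.09n) responders.

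- n = 130: 13 + 6.70 = 19.70, so 20. The exact test needs 21 (tail probability 0.034 at 20, 0.019 at 21).
- n = 185: 18.5 + 8.00 = 26.50, so 27. The exact test needs 28 (tail probability 0.030 at 27, 0.018 at 28).

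**4. What the expanded regimen must achieve.** Take 1 responder in the 35 and, as an assumption, 2 in the other 20. On the pooled set the expanded regimen needs 27 − 3 = 24 of 130 (18.5%) instead of 20 (15.4%) by z-test, or 28 − 3 = 25 (19.2%) instead of 21 (16.2%) by exact test. Both pooled requirements exceed the planned alternative of 18%.

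**5. Power, by exact enumeration.** Let A ~ Bin(20, 0.18) be responders in the dose group that is expanded, Y ~ Bin(110, 0.18) those in the expansion, and B ~ Bin(20, q) those in the other new group. The first part is fixed at 1. An ORR above 15% in 20 subjects means A ≥ 4, which has probability 0.497. Given A ≥ 4:

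| Quantity | z-test | Exact test |
|---|---|---|
| Power on the 130 | 90.1% | 84.9% |
| Power on the 185, q = 5% | 51.7% | 42.5% |
| Power on the 185, q = 10% | 60.7% | 51.7% |
| Power on the 185, q = 15% | 68.9% | 60.5% |
| 130 succeeds and 185 fails, q = 5% | 38.4% | 42.4% |
| 130 succeeds and 185 fails, q = 10% | 29.4% | 33.2% |
| 130 succeeds and 185 fails, q = 15% | 21.3% | 24.5% |

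**6. Sensitivity.**

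- Two responders in the first part: power on the 185 is 69.3% (60.9–76.6% over q = 5–15%) by z-test and 60.7% (51.7–68.9%) by exact test.
- Other group required to miss the threshold (B ≤ 3, q = 10%): 57.6% by z-test, 48.3% by exact test.
- Other group at 18%: 73.4% by z-test.
- No conditioning on the expansion rule, q = 10%: 48.2% on the 185 against 81.2% on the 130, by z-test.

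**7. Type I error.** With the expanded regimen truly at 10% and the expansion rule included, the probability of expanding and rejecting on the 185 is 0.0008–0.0040 (z-test) or 0.0004–0.0022 (exact) for q = 5–15%. On the 130 it is 0.0142 (z-test) or 0.0085 (exact).

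**The case against.** The strongest reply is that the document already identifies the set by count. The hypotheses, the success criterion and the 130 stand together in 10.3; 20+110 fits only one dose group plus its expansion; and the expansion rule is stated by dose group. The synopsis calls for results by treatment arm, section 8.3 randomizes the two new groups, and section 10.1 leaves final methods to a separate SAP. No passage states 185 or says that doses will be pooled. The loss of power is a scenario: it needs the trial to expand and the analyst to disregard 10.3, and it rests on an interim 1/35 and an assumed rate in the other group. The error is also conservative.

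Much of this stands. Pooling is the literal consequence of 10.2.1 and 10.6.1, not a declared plan. The figures conditional on expansion should not be read against the 80% in 10.3, although the unconditional gap is wider (step 6). The type I statement was checked for 5–15% in the other group; at 30% the z-test rejection probability on the 185 is about 0.019, above the 0.0142 on the 130 but still below 0.025.

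It does not remove the contradiction. A count in a sizing paragraph does not amend a population definition. The synopsis line governs tabulation and does not say which arm is tested, while 10.2.1 calls the study single-arm. The SAP deferral names no set, and nothing in the supplied text fills the gap. The per-protocol set is drawn from all treated subjects and has the same fault. What happens if both new groups exceed 15% is a separate gap.

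**Conclusion.** The concern holds. The sample size in 10.3 is right for 130, but the definition in 10.2.1 and the test in 10.6.1 describe about 185, and no text reconciles them. This is a contradiction about the set for the primary hypothesis test, not merely missing detail, and it must be fixed.

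If the definition is followed literally, z-test power in expanded trials falls from 90.1% to 60.7% (51.7–68.9%), and exact-test power from 84.9% to 51.7% (42.5–60.5%). About three expanded trials in ten would succeed on the 130 and fail on the 185. These figures assume a true 18% ORR in the expanded regimen, one expansion of 110, the interim 1/35 taken as final although one subject was not yet evaluated, and 10% (5–15%) in the other new group. That last rate is not given in the documents. The harm is lost power and an ambiguous primary result, not a raised false-positive rate.

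**What to change.** In 10.2.1, define a separate primary efficacy set: treated subjects whose starting regimen is the expanded regimen, from the second part (20) and the expansion (110). In 10.3, attach the hypotheses and the 130 to that set by name. In 10.6.1, apply the one-sample test to that set only. Report the 15 mg, 30 mg and unexpanded groups descriptively by dose. Keep the Treated population, all dosed subjects, for safety.

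The cost is one definition and one phrase in each of two sections. Enrolment, visits and data collection do not change. It should be settled before the expansion starts.

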10.2.2 Per-Protocol Population

The per-protocol population consists of all treated subjects who met all eligibility criteria and received at least 80% of doses during Cycle 1, and have at least one postbaseline tumor assessment. The primary and secondary efficacy endpoints will also be analyzed based on the Per-protocol population and considered as supportive for this study.

10.3 Sample Size and Power Considerations

For the primary efficacy endpoint, ORR, the sample size is based on one-sample binomial test with normal approximation. The null hypothesis to be tested is that the ORR (defined as the proportion of subjects with at least a partial response (PR) based on the Treated population subjects) is $\leq 10\%$; the alternative hypothesis is that the ORR is $\geq 18\%$. With these hypotheses, a sample size of 130 (20+110) subjects in the Treated population would provide 80% power at a one-sided 0.025 significance level. This criterion requires that the lower limit of the 95% confidence interval (CI) for the ORR is greater than 10%.

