4. OVERALL STUDY DESIGN

4.1 Study Design

ATG-008-HCC-001 is a MRCT trial in which ATG-008 will be administered orally in HBV+ HCC subjects who have received at least one prior line of systemic therapy in Asian countries. The trial is designed as an open-label phase 2 trial to assess PK, safety, tolerability and efficacy of oral ATG-008 administered until the appearance of radiologic disease progression (according to RECIST 1.1). The PK and safety profiles will be compared with historical ATG-008 results when

data are available.

According to the previous study results, the sponsor will plan to continue to enroll approximately 40 hepatitis B virus (HBV) positive, unresectable HCC subjects who have previously received at least one prior line of systemic therapy. Among which, approximately 20 subjects will receive oral ATG-008 at an initial dose of 45 mg/QD and another 20 subjects will receive oral ATG-008 at an initial dose of 20mg/BID. The pharmacokinetic (PK) samples will be collected from 10 subjects each in the two dose groups so as to further evaluate the PK profile of ATG-008 and its metabolites.

If the overall response rate (ORR) of tumor is greater than 15% in the study dose group (45 mg/QD or 20 mg/BID), then this study will be expanded to enroll additional approximately 110 subjects using ORR as the primary study endpoint, to further evaluate the efficacy and safety of ATG-008.

At the discretion of the Investigator, treatment may continue beyond radiologic progression until symptomatic deterioration if no other therapeutic options are available. Subjects may also receive best supportive care according to local practice. All subjects will continue to be followed after treatment discontinuation for radiologic tumor response until disease progression, death or withdrawal of consent (as defined in Section 6.4, if applicable) and new anticancer treatments until death or withdrawal of consent. Subjects will also be followed for survival until death or withdrawal of consent.

[figure not shown]
The starting dose of ATG-008 will be 15 mg daily for 28 days each cycle for the first 6 fully evaluable (including PK outcomes) subjects. Providing DLTs occur in less than 2 of 6 subjects who complete Cycle 1, additional 24 subjects will be enrolled at the starting dose of 30 mg daily. Subjects who tolerated the 15-mg dose level for at least 1 cycle may then dose-escalate to 30 mg at the Investigator's discretion.

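### Section 10.3's 80% power ignores the ORR >15% expansion gate; with the gate binding at 4 of 20, a dose at 18% ORR expands and succeeds with probability 39–45%

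*Combined protocol and SAP*

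**What the plan says.** Section 10.3 sizes the primary efficacy test of ORR: "the sample size is based on one-sample binomial test with normal approximation". The null is an ORR of at most 10%, the alternative at least 18%, and the claim is that "a sample size of 130 (20+110) subjects in the Treated population would provide 80% power at a one-sided 0.025 significance level". Success is defined as "the lower limit of the 95% confidence interval (CI) for the ORR is greater than 10" per cent.

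The split 20+110 reflects a two-step design. Section 4.1 says "approximately 20 subjects will receive oral ATG-008 at an initial dose of 45 mg/QD and another 20 subjects" will receive 20 mg BID. Section 10.1 then says: "If ORR of tumor is greater than 15% in the study dose group (45 mg/QD or 20 mg/BID), this study will be expanded" by about 110 subjects. The same rule appears in the synopsis (Study Population and Study Treatments) and in Sections 4.1, 4.2, 6.4.1 and 7.1. Because the 130 is written as 20+110, the gate subjects are also part of the final test.

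Section 10.6.1 says "ORR will be summarized with 95% confidence interval (CI), and tested using one sample binomial test for the Treated population", without naming the interval method. Section 10.1 leaves the final methods to the SAP.

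**The concern.** A one-step power formula is applied to a procedure with two steps. The final test is run for a dose only if that dose first passes the 15% gate, and nothing in Section 10.3 reports the chance of passing or the power of the two steps together. No section describes expansion at 15% or below, calls the gate advisory, or says that the 80% is conditional on expansion.

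A reader of Section 10.3 would conclude that a dose at the target ORR of 18% has a 20% risk of being missed. If the gate removes such a dose about half the time, the real risk is much larger, and the decision on committing a further 110 patients is being made on an operating characteristic that the design does not have.

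**Working it through.** **Inputs.** From Section 10.3: p0 = 0.10, p1 = 0.18, n = 130 = 20 + 110, one-sided α = 0.025, success when the lower 95% limit exceeds 10%. From Section 10.1: gate at observed ORR above 15%. Assumed: the gate is binding, there are exactly 20 gate subjects, and the same response calls are used at the gate and the final test.

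**1. The plan's own figure.** With null variance for α and alternative variance for β:

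n = [(1.960·√(0.10·0.90) + 0.842·√(0.18·0.82)) / 0.08]² = 129.8, so 130.

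Power at 130 = Φ[(0.08 − 1.960·√(0.09/130)) / √(0.1476/130)] = Φ(0.844) = 80.06%.

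The stated 80% is reproduced. The formula has no term for the gate.

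**2. Success count out of 130.** This depends on the interval method.
- Score/normal: z = (20/130 − 0.10)/√(0.09/130) = 2.046, above 1.960, so 20 responders.
- Exact (Clopper-Pearson): lower limit 0.0966 at 20 and 0.1029 at 21, so 21.
- Wald: lower limit 0.0983 at 21 and 0.1048 at 22, so 22.

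**3. The gate.** 3/20 = 15.0% is not greater than 15%, so at least 4/20 is needed.
- P(Bin(20, 0.18) ≥ 4) = 49.7%, so a dose at target is not expanded with probability 50.3%.
- P(Bin(20, 0.10) ≥ 4) = 13.3%.

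**4. Both steps together.** For success count c, by exact enumeration:

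P(expand and succeed) = Σ over x = 4 to 20 of P(Bin(20, p) = x) · P(Bin(110, p) ≥ c − x).

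| | Score/normal, c = 20 | Exact, c = 21 | Wald, c = 22 |
|---|---|---|---|
| Ungated exact power at 18% | 81.2% | 74.2% | 66.0% |
| **Expand and succeed at 18%** | **44.8%** | **42.2%** | **38.9%** |
| Power given expansion | 90.1% | 84.9% | 78.2% |
| Type I error at 10%, ungated | 0.034 | 0.019 | 0.010 |
| Type I error at 10%, gated | 0.014 | 0.009 | 0.005 |

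A simulation of 2,000,000 trials gave the same 44.8%, 42.2% and 38.9%. The true ORR would have to be about 26% for the two steps together to reach 80%.

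**5. Sensitivity, at 18% ORR.**
- *Gate of 18 to 22 subjects* (my range for approximately 20): 38.9–60.1% with the total held at 130, and 38.9–59.5% with exactly 110 added. The top of each range is at 19, where 3/19 = 15.8% passes.
- *3/20 allowed through*: the chance of expanding rises to 72.5%; expand and succeed is 62.8%, 58.4% or 52.9%.
- *Both doses at 18% and free to expand independently* (not stated in the protocol): P(at least one succeeds) = 1 − (1 − w)², where w is the per-dose figure in step 4. This gives 69.5%, 66.6% or 62.6%.
- *Gate not binding, with a failed gate overridden a fraction f of the time*: solve w + f·(ungated − w) = 0.80. For score/normal, f = (0.80 − 0.4481)/(0.8121 − 0.4481) = 96.7%. For exact or Wald, f would exceed 1, so 80% cannot be reached.

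**The case against.** The strongest reply is that the sentence in Section 10.3 is true as it stands. It describes a test on 130 treated subjects and makes no claim about the chance of reaching 130. When that test is run, power given expansion is 90.1% or 84.9%, and falls just below 80% (78.2%) only under Wald. That much is correct. But Section 10.3 does not present the 80% as conditional, and it is not the conditional figure under any of the three methods.

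Other points have some force:
- Exactly 20 is the least favourable denominator in the range, because 3/20 falls on the threshold.
- The rule says if, not only if, so a binding gate is an assumption.
- Two doses are tested, so the trial has up to two chances.
- Wald limits are named nowhere. The sizing formula matches the score/normal count of 20, which gives 44.8%.

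Each of these moves the figure, and step 5 shows by how much. None brings it to 80%, short of overriding almost every failed gate under the score/normal criterion. Leaving final methods to the SAP does not help either, because the power claim and the gate are already in the protocol. It is fair to say that naming the interval method and the response read would, taken alone, be requests for missing detail.

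**Conclusion.** The concern holds. The 80% is the power of a fixed test on 130 subjects. For the gated 20+110 procedure, with the gate binding at 4 of 20, a dose at 18% ORR expands and succeeds with probability 39–45%. The false-negative risk is therefore 55–61% per dose, against the 20% that the stated power implies. The 49.7% chance of expanding alone caps success below one half, whatever final test is chosen.

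These figures are per dose and assume a binding gate, exactly 20 gate subjects and the same response calls at both steps. Relaxing the gate size, the treatment of 3/20 or the one-dose view gives 39–60%, 53–63% and 63–70% respectively, all below 80%. The gate reduces type I error, so no false-positive problem arises. This should be fixed, because the protocol states a property that its two-step design does not have.

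**What to change.** In Section 10.3:
1. Label the 80% as fixed-sample power that ignores the gate. Add, per dose, the chance of expanding and the two-step power at 18% ORR, and the two-step type I error at 10%. For a binding gate of 20 these are 49.7%; 44.8%, 42.2% or 38.9%; and 0.014, 0.009 or 0.005 (score/normal, exact or Wald).
2. Name the final test or interval method and its success count out of 130.
3. State the gate as a count over a fixed denominator. Under the current wording that is at least 4 of the first 20 Treated subjects at that dose. Carry this into each place where the 15% rule is repeated.
4. State which read applies at the gate and at the final test, and whether responses must be confirmed. Section 6.4.1 describes investigator RECIST 1.1 assessment, confirmation at the next scheduled scan, and central review, but does not assign them to the two steps. Note that the two-step figures assume the same response calls at both.

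The cost is wording and recalculated figures. No extra patients, earlier central reads, or change of threshold or sample size is needed. The stated power will look less favourable.

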10.6.2 Analysis of the Secondary Efficacy Endpoints

Overall Survival is defined as the time from the first dose date until death. A subject who has not been reported as a death will be censored at the last available date the subject is known to be alive, or the clinical cut-off date, whichever is earlier.

Time to progression (TTP) will be calculated as the time from the first dose date to disease progression. Subjects who do not have disease progression will be censored at the date of the last tumor assessment that the subject was progression free, or the clinical cutoff date, whichever is earlier.

Progression free survival (PFS) is defined as the time from the first dose date to the date of disease progression according to RECIST 1.1 or death (due to any cause) on or prior to the clinical cutoff date, whichever occurs earlier. Subjects who do not have disease progression or have not died will be censored at the date of the last tumor assessment that the subject was progression free on or prior to the clinical cutoff date.

Disease control rate (DCR) is defined as the percentage of subjects with complete (CR), or partial response (PR) or stable disease (SD).

For responders, time to response (TTR) and response duration will be analyzed.

TTR is the time from the first dose date to the first documentation of response of PR or better. TTR will be summarized for responders using summary statistics.

Duration of response (DOR) is defined as the time from the time when criteria are first met for CR/PR (whichever is first recorded) until the first date that recurrent or progressive disease is objectively documented for responders. DOR will be censored using the same censoring rules as used for PFS.

Survival rate is defined as the Kaplan-Meier estimated proportion of subjects surviving at 6, 9, 12 months.

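### With 130 treated subjects no responder cut-off gives both 80% power and one-sided 0.025, and the plan does not say whether 20/130 is a success

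*Combined protocol and SAP*

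**What the plan says.** Section 10.3 sets a null ORR of at most 10% against an alternative of at least 18%. It says that "the sample size is based on one-sample binomial test with normal approximation" and concludes that "a sample size of 130 (20+110) subjects in the Treated population would provide 80% power at a one-sided 0.025 significance level". The success rule follows: "This criterion requires that the lower limit of the 95% confidence interval (CI) for the ORR is greater than 10" per cent. No interval method and no responder count are given.

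Section 10.6.1 says ORR will be summarised with a 95% CI and "tested using one sample binomial test for the Treated population analyzed in a similar way as for DCR". It does not say whether the binomial test is exact or approximate. The DCR pointer leads to section 10.6.2, which defines DCR but gives no test or interval for it. Section 10.1 leaves the final methods to the SAP; the document supplied contains no further detail on this point.

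The 130 consists of one dose group of about 20 plus about 110 more, who are enrolled only if ORR in that group exceeds 15% (sections 7.1 and 10.1).

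**The concern.** There are two linked problems. First, the power and significance level in 10.3 come from a continuous approximation, while the decision rests on an integer count. If no integer cut-off meets both, the stated pair describes no rule that can be applied to 130 subjects.

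Second, the success criterion is a CI limit with no CI method, and the test is named only by family. Common methods disagree close to the 10% boundary. This is the only hypothesis test on the primary efficacy endpoint of an open-label trial, so if the method were fixed after responses are known, that choice could decide the result.

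**Working it through.** **Inputs.** From section 10.3: p0 = 0.10, p1 = 0.18, one-sided α = 0.025, power 80%, n = 130. The denominator is all treated subjects (section 10.2.1), so no dropout allowance is needed.

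**Reproducing 130.** With the null variance in the α term and the alternative variance in the power term:

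n = [(1.96·√(0.10·0.90) + 0.8416·√(0.18·0.82)) / 0.08]² = 129.77, rounded up to 130. Nominal power at 130 is 80.06%. The continuity-corrected version of the formula gives 142.

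**Exact tails at n = 130.** Error is P(X ≥ r | 0.10) and power is P(X ≥ r | 0.18), with X binomial:

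| Responders needed | Type I error | Power |
|---|---|---|
| ≥19 | 5.96% | 87.0% |
| ≥20 | 3.44% | 81.2% |
| ≥21 | 1.89% | 74.2% |
| ≥22 | 0.99% | 66.0% |

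Both columns fall as the cut-off rises. The step from 20 to 21 takes the error below 0.025 and the power below 80% together, so no cut-off meets both. With cut-off 21, power reaches 80% only at a true ORR of about 18.7%.

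**What each method says at 20/130 (15.4%).**

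- Score test without continuity correction: z = (20/130 − 0.10)/√(0.09/130) = 2.046, one-sided p = 0.020: success.
- With continuity correction: z = (19.5/130 − 0.10)/√(0.09/130) = 1.900, p = 0.029: failure.
- Exact binomial: p = 0.034: failure.
- 95% lower limits: Wilson 10.19% (success); Clopper-Pearson 9.66% (failure); Wald 9.18% (failure).

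At 21/130 the Clopper-Pearson limit is 10.29% (success) but the Wald limit is 9.83% (failure). Wald first succeeds at 22.

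**How likely is exactly 20/130?** For a fixed sample, 7.1% at ORR 18%, with a maximum of 9.7% near ORR 15.4%.

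**Other sample sizes.** The additional enrolment is only approximate. For n = 125 to 135, the exact and score rules need the same count only at 125 and 133. At the other nine sizes the score rule's error is 2.6% to 4.0%. Exact power over this range is 68.7% to 77.8%. No n from 120 to 140 meets both targets; the smallest that does is 141 with at least 22 responders (error 2.39%, power 80.07%).

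**Adding the expansion gate.** Assume exactly 20 in one dose group, so that >15% means at least 4/20, with those 20 pooled into the 130. The gate is passed with probability 49.7% at ORR 18% and 13.3% at ORR 10%.

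| Final cut-off | Gate and success at ORR 10% | Gate and success at ORR 18% |
|---|---|---|
| ≥20 | 1.42% | 44.8% |
| ≥21 | 0.85% | 42.2% |

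The chance of passing the gate and ending at exactly 20/130 at ORR 18% is 44.8% − 42.2% = 2.6%.

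**The case against.** The best defence is that 10.3 openly describes an approximate calculation and is correct on that basis. Only the uncorrected formula gives 130, which points to the uncorrected score test for the analysis, and under that test 20/130 succeeds. The 3.4% error also belongs to a fixed sample the trial does not use: once the gate applies, the score rule's error is 1.42% per dose group, and the ungated 7% for exactly 20/130 falls to 2.6%. Finally, the SAP is where such detail would normally be settled.

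Much of this is fair. The sizing formula is valid, section 10.6.1 does name the test family, and the gate does lower the error for one dose group. But reading the uncorrected test into the analysis leaves the CI criterion open: at 20/130 that test passes while a Wald or Clopper-Pearson interval fails, although 10.3 treats level and interval as one rule. The gate also cuts the chance of success at ORR 18% to below 45%, so it does not rescue the 80%. If both dose groups could expand independently, the chance of at least one false success under the 20-responder rule is about 2.8%. Naming a method in the SAP would settle 20/130 but would not make the stated pair true.

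**Conclusion.** The concern holds. In a fixed sample of 130 the sponsor has either about 74% power with the error held to 0.025 (at least 21 responders), or about 81% power with an error of 3.4% (at least 20), not the combination in 10.3. The result 20/130 depends on an unnamed method, and 21/130 does too if a Wald interval is admitted. These figures need only the hypotheses and sample size in 10.3. The gated figures rest on the assumptions of exactly 20 subjects, at least 4 responders and pooling; under them the stated pair still fails, because power is 42% to 45%. The point should be corrected, although the formula behind 130 is sound.

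**What to change.** In 10.3 and 10.6.1 name one test with its matching interval, applied to the number actually treated in the expanded dose group, and delete the DCR comparison in 10.6.1. Two consistent choices are available.

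- **Exact rule, holding 0.025.** Suggested text for 10.6.1: *ORR will be tested with the exact one-sided binomial test of ORR ≤10% at 0.025, with the two-sided Clopper-Pearson 95% CI. Success is a lower limit above 10% (at least 21 responders if exactly 130 are treated).* Restate 10.3 as: *nominal 80% power by normal approximation; exact fixed-sample power about 74% at ORR 18% (80% at about 18.7%), type I error 1.9%.*
- **Score rule.** Specify the score test without continuity correction and the Wilson 95% CI (at least 20/130), and state the fixed-sample error of 3.4% and power of 81%.

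In either case add: *These figures exclude the >15% ORR expansion gate*, so that 74% or 81% is not read as the chance of success from the start.

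The cost is wording in two sections, with enrolment unchanged. The downside is a less favourable stated power under the exact rule, or an openly stated error above 0.025 under the score rule. Meeting both targets exactly on a fixed-sample basis would take at least 141 treated subjects, which is a change of enrolment and not of wording.
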